9.5.2 Immunogenicity Analysis Populations

Per-Protocol Immunogenicity (PPI) Population

The PPI population will serve as the primary population for the analysis of immunogenicity in this study. To be included in this population, participants must satisfy all the criteria for the PPE population, and additionally must:

- 1. Have received all vaccinations within acceptable day ranges (see Table 4)
- 2. Have provided blood samples for serology testing within the acceptable day range (see Table 5)

PROTOCOL/AMENDMENT NO.: 064-03

All Naïve Participants with Serology (ANPS)

A supportive analysis of immunogenicity will be conducted on the ANPS population. To be included in this population, participants must:

- 1. Have received at least 1 vaccination
- 2. Have provided serum samples with evaluable results
- 3. Be seronegative at Day 1 and PCR-negative from Day 1 through Month 7 to the appropriate HPV type(s).

Participants who receive incorrect clinical material or an incorrect dose of vaccine will be included in the analysis in the group to which they were randomized.

Dose of the 9vHPV Vaccine Scheduled for Injection	Protocol Specified Visit Window	Day Range for Inclusion in Statistical Analysis (Relative to Day 1†)				
Dose 1	Day 1 [†]	0				
Dose 2	Month 2 ± 3 weeks	36 to 84				
Dose 3	Month 6 ± 4 weeks	148 to 218				
† Day 1 refers to the date when dose 1 of the 9vHPV vaccine is injected						

Table 4 Acceptable Day Ranges for Vaccination Visits

Table 5 Acceptable Day Ranges for Collection of Serum Samples

Study Visit	Sample Type	Target Collection Day (Relative to Day 1†)	Day Range for Inclusion in Statistical Analysis (Relative to Day 1†)
Day 1	Serum	0	-14 to 0
Month 7	Serum	30 days post dose 3	21 to 49 post dose 3
Month 36	Serum	1095	913 to 1277

Day 1 refers to the date when dose 1 of the 9vHPV vaccine is injected. For Month 7, indicated target collection/day range is relative to date of injection of dose 3 of the 9vHPV vaccine.

9.5.3 **Safety Analysis Population**

Safety analyses will be conducted in the APaT population, which consists of all randomized participants who received at least 1 dose of the 9vHPV vaccine or placebo and have provided safety data at any time during the study. Participants will be included in the treatment group corresponding to the study treatment they actually received (i.e., 3 doses of vaccine or 3 doses of placebo). For participants who received injections of vaccine and placebo (i.e., cross-treated participants) corresponding to a regimen that does not correspond to any of the protocol-defined vaccination groups (i.e., not 3 doses of vaccine nor 3 doses of placebo), a safety profile listing will be created separate from the safety reports that will be provided for the protocol-defined vaccination groups.

9.6 Statistical Methods

Statistical methods for efficacy and immunogenicity analyses are described in Section 9.6.1 and Section 9.6.2, respectively. The same analysis plan for analysis populations and methods without hypothesis testing will be applied to evaluate decreasing of selected efficacy and immunogenicity endpoints from the first database lock for primary analysis, by using data up to the end-of-base-study (the database lock after the completion of the final efficacy sample assessment for the final efficacy analysis and after the last participant's Final Visit in the base study for the final immunogenicity and safety analysis). Safety analysis approaches are described in Section 9.6.3. Selected safety endpoints will be summarized separately using descriptive methods for Tier 3 events in an end-of-base-study report. Only SAE/death will be summarized separately using descriptive methods in an extension study report. Methods related to exploratory objectives will be further described in the sSAP.

9.6.1 Statistical Methods for Efficacy Analyses

For each of the primary and secondary efficacy objectives, the hypothesis that VE is greater than 0% will be tested.

The null and alternative hypotheses to be tested are:

H₀: $VE \le 0\%$

H₁: VE >0%;

where VE is defined as:

$$VE = 100\% * \{1-(Rv/Rp)\}$$

and Rv and Rp are the incidence rates of the relevant efficacy endpoint in the 9vHPV vaccine and placebo groups, respectively. VE is equivalent to the percent reduction in the risk of becoming a case of an efficacy endpoint in the 9vHPV vaccine group relative to the risk in the placebo group. The incidence rate Rv is defined as Rv = Cv/Tv, where Cv = the count of the relevant efficacy endpoint cases in the vaccine group and Tv = total person-years of follow-up for efficacy in the vaccine group. The incidence rate Rp is defined similarly.

The hypothesis that VE is greater than 0% will be tested by constructing a $100*(1-\alpha)$ % CI for VE with respect to the relevant efficacy endpoint, denoted as (VE_L, VE_U). The test of hypothesis will be declared successful if VE_L >0%.

Generally, the $100*(1-\alpha)$ % CI for VE, (VE_L, VE_U), will be computed as follows. Under the assumption that Rv and Rp are the means of independent Poisson processes, and given that there is a total of n = Cv + Cp efficacy endpoint cases observed across 2 vaccination groups, then the number of efficacy cases Cv in the 9vHPV vaccine group is distributed as Binomial(n,π), where the binomial probability π is defined as:

$$\pi = \text{TvRv}/(\text{TvRv} + \text{TpRp})$$

PRODUCT: V503 PROTOCOL/AMENDMENT NO.: 064-03

The probability π is a person-years-adjusted estimate of the probability that a particular participant who became a case of the relevant efficacy endpoint belongs to the 9vHPV vaccine group. The lower bound of the $100*(1-\alpha)$ % exact CI for the probability π is obtained by searching for the proportion π_L such that the probability of observing Cv or more efficacy endpoint cases out of n total efficacy cases is $\leq \alpha/2$. Similarly, the upper bound of the $100*(1-\alpha)$ % exact CI for the probability π is obtained by searching for the proportion π_U such that the probability of observing Cv or fewer efficacy endpoint cases out of n total efficacy cases is $\leq \alpha/2$ [Chan, I. S. F. and Bohidar, N. R. 1998]. VE_L and VE_U are then calculated from π_L and π_U as follows:

$$\begin{split} VE_L &= 100\% * \{1 - \pi_U (1 + \theta)\} / (1 - \pi_U); \\ VE_U &= 100\% * \{1 - \pi_L (1 + \theta)\} / (1 - \pi_L); \end{split}$$

where $\theta = \text{Tp/Tv}$ is the ratio of the total person-years of follow-up for efficacy in the placebo group over the 9vHPV vaccine group.

The efficacy analyses strategy are summarized in Table 6.

Table 6 Analysis Strategy for Efficacy Variable

Endpoint/Variable (Description, Time Point)	Primary vs. Supportive Statistical Approach Method		Analysis Population	Missing Data Approach				
Primary Efficacy Hypothesis								
HPV 6/11/16/18-related anogenital	Point estimate, 95% P CI and p-value by exact method		PPE	Observed data only				
persistent infection	S	Point estimate and 95% CI by exact method	HN-TS	Observed data only				
	Secondary Efficac	y Hypothesis						
HPV 31/33/45/52/58-related	P	Point estimate, 95% CI and p- value by exact method	PPE	Observed data only				
anogenital persistent infection	S	Point estimate and 95% CI by exact method	HN-TS	Observed data only				

9.6.2 Statistical Methods for Immunogenicity Analyses

9.6.2.1 Estimation of GMTs

Anti-HPV 6, 11, 16, 18, 31, 33, 45, 52, and 58 antibody GMT and the corresponding 2-sided 95% CI will be evaluated at 1 month post last dose (Month 7) by vaccine group. For this purpose, the mean and corresponding 95% CI of the natural logarithm of the anti-HPV titers will be calculated and exponentiated to generate the GMT and the corresponding 95% CI. The 95% CI of the mean of the natural logarithm of anti-HPV titers will be constructed based on the t-distribution. Reverse cumulative distribution (RCD) plots will be provided for graphical representation of distributions of HPV titers at Month 7.

Anti-HPV titers reported as less than the LLOQ of the relevant anti-HPV type will be replaced by the half of the LLOQ in the numerical computation of GMT.

9.6.2.2 Estimation of Percent Seroconversion

The percent seroconversion with respect to anti-HPV 6, 11, 16, 18, 31, 33, 45, 52, and 58, at Month 7 will be evaluated by computing point estimates and corresponding 2-sided 95% CIs by vaccine group. Calculation of the 95% CI of percent seroconversion will be based on the exact binomial method proposed by Clopper and Pearson [Clopper, C. J. and Pearson, E. S. 1934].

9.6.3 Statistical Methods for Safety Analyses

Safety and tolerability will be assessed by clinical review of all relevant parameters including AEs and postvaccination temperature measurements. The analysis of safety results will follow a tiered approach (Table 7). The tiers differ with respect to the analyses that will be performed. AEs (specific terms as well as system organ class terms) are either pre-specified as "Tier 1" endpoints or will be classified as belonging to "Tier 2" or "Tier 3" based on the observed proportions of participants with an event. The safety analysis strategy is summarized in Table 7.

Tier 1 Events

Safety parameters or AEs of special interest that are identified a priori constitute "Tier 1" safety endpoints that will be subject to inferential testing for statistical significance. There are no Tier 1 events for this protocol based on the global safety data on the 9vHPV vaccine.

Tier 2 Events

Tier 2 parameters will be assessed via point estimates with corresponding 95% CIs provided for the differences in the proportion of participants with events (using the Miettinen and Nurminen method [Miettinen, O. and Nurminen, M. 1985]). Membership in Tier 2 requires that at least 1% of participants in any treatment group exhibit the event.

In addition to individual events that occur in at least 1% of participants in any treatment group, the broad AE categories consisting of the proportion of participants with SAEs during

Days 1 through 15 postvaccination, vaccine-related SAEs observed any time during the study, and elevated temperatures (≥37.5°C) will be considered Tier 2 endpoints. The proportion of participants with solicited injection-site AEs (pain/tenderness, swelling, and redness) and severe injection-site AEs during Days 1 through 5 postvaccination will also be included in Tier 2 endpoints. Detailed endpoints and day ranges are summarized in Table 7.

Tier 3 Events

Safety endpoints that are not Tier 1 or 2 events are considered Tier 3 events. Only point estimates (counts and percentages) by vaccination group are provided for Tier 3 safety parameters. Safety analyses will be based on the observed data (i.e., with no imputation of missing data).

Table 7 Analysis Strategy for Safety Parameters

Safety Tier	Safety Endpoint (a)	95% CI for Comparison of 9vHPV to Placebo	Descriptive Statistics
Tier 2	Injection-site pain/tenderness, swelling, and redness during Days 1 through 5 postvaccination	X	X
	Other injection-site AEs (incidence ≥1% of participants in either group) during Days 1 through 5 postvaccination	X	X
	Severe injection-site AEs (b) during Days 1 through 5 postvaccination	X	X
	Systemic AEs (incidence ≥1% of participants in either group) during Days 1 through 15 postvaccination	X	X
	Elevated temperatures (c) during Days 1 through 5 postvaccination	X	X
	SAEs during Days 1 through 15 postvaccination	X	X
	Serious vaccine-related AEs observed any time during the study	X	X
Tier 3	AEs by SOC		X
	Maximum intensity rating for each category of injection- site AEs		X
	Maximum intensity rating, over all systemic AEs		X
	Maximum temperatures		X
	New medical conditions		X

Abbreviations: AE=adverse event, SAE=serious adverse event, SOC=System Organ Class

- (a) The day of vaccination is counted as Day 1. Day ranges for endpoints are as follows: injection-site AEs and maximum temperatures Days 1 through 5 postvaccination; systemic AEs Days 1 through 15 postvaccination.
- (b) For the injection-site redness and swelling 0 to 2.5 cm (0 to 1 inch) will be categorized as mild, >2.5 to 5 cm (>1 inch to 2 inches) will be categorized as moderate, and >5 cm (>2 inches) will be categorized as severe.
- (c) Defined as maximum (over the follow-up period) temperature $\ge 37.5^{\circ}$ C.

Note: X = indicated summary statistic will be provided.

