Participants will be followed for solicited injection-site AEs Days 1 through Days 5 following each vaccination, and any other injection-site AEs and systemic AEs Days 1 through Days 15 following each vaccination. Any SAEs regardless of causality will be recorded from the time of randomization through 6 months postdose 3. Vaccine-related SAEs and deaths will be collected throughout the study. New medical conditions (defined as incident medical conditions occurring outside of Days 1 to Days 15 period following each vaccination and not considered SAEs) will be recorded for all participants at each study visit throughout the study.

The primary analysis is case driven. The database will be locked, and the primary analysis will be conducted after at least 17 primary efficacy endpoint cases and at least 17 secondary efficacy endpoint cases have been observed in the base study. There is no interim analysis planned in this study. These efficacy results as well as immunogenicity and safety results based on data in the initial database lock for the primary analysis will be reported as the primary CSR. All participants will be unblinded after the primary efficacy analysis database lock. Once a participant is unblinded, no further efficacy samples will be collected from the participant.

Once at least 17 primary endpoint cases and at least 17 secondary efficacy endpoint cases are accrued, each participant will proceed to the Final Visit promptly without completing any other scheduled visits in order to complete the base study (as shown in Section 1.3, and Section 8.12.1.4). Additional database locks will be executed, including a second database lock after the completion of the final efficacy sample assessment for the purpose of the final efficacy analysis and a final database lock of the base study after the last participant's Final Visit in the base study for the final immunogenicity and safety analysis, respectively. Cumulative data collected from the initiation of the study will be summarized separately and a report will be written after each database lock. The base study will end after the last participant completes their Final Visit in the base study.

Extension Study

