The investigator or delegate will train the participant in the use of the VRC at Visit 1 (Day 1). Temperatures, injection-site reactions, other complaints or illnesses, and concomitant medications or vaccinations will be recorded on the VRC by the participant. Participants should be informed to contact the investigator immediately in the event of a hospitalization or visit to another physician.

V503-064-03 FINAL PROTOCOL 24-SEP-2024 Confidential

Participants will use the VRC to document the following information:

- Oral temperatures measured Day 1 (day of vaccination) through Day 5 postvaccination.
 - Participants will record oral temperature in the evening after each study vaccination and daily, at the same time of day, for 4 days after each study vaccination for the purpose of identifying febrile events.
 - Note: If an oral temperature indicates a fever (defined as an oral temperature of ≥ 37.5 °C), the AE of "fever" must be documented in the appropriate eCRF.
- Solicited injection-site AEs (redness/erythema, swelling, and tenderness/pain) Day 1 through Day 5 postvaccination.
- Any other injection-site or systemic AEs Day 1 through Day 15 postvaccination.
- Concomitant medications and non-study vaccinations Day 1 through Day 15 postvaccination.

In order to ensure that the VRC is being filled out without delay, telephone contacts to remind the participant will be conducted after 15 days postvaccination.

All participants will be expected to bring the VRC to the study site at the next scheduled visit. The investigator or delegate will review the data captured on the VRC with the participant at Visit 2 (Month 2), Visit 3 (Month 6), and Visit 4 (Month 7). For the AEs outlined above, the investigator will use the information provided by the participant both on the VRC, and verbally at the time of VRC review, to apply the appropriate assessment of causality as described in Appendix 3. At the time of VRC review at the next scheduled visit, participants will be questioned regarding any new medical conditions that occurred beyond Day 15 postvaccination. The investigator will determine if the medical condition is to be reported as an SAE using the reporting guidelines provided in Section 8.4.

Extension Study:

A VRC will not be utilized for participants enrolled in the extension study and NSAEs will not be collected. SAEs and death will be collected from the first dose of vaccination until 1 month after the last dose.

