8.5 Adverse Events, Serious Adverse Events, and Other Reportable Safety Events

The definitions of an AE or SAE, as well as the method of recording, evaluating, and assessing causality of AE and SAE and the procedures for completing and transmitting AE, SAE, and other reportable safety event reports can be found in Appendix 3.

Adverse events, SAEs, and other reportable safety events will be reported by the participant (or, when appropriate, by a caregiver, surrogate, or the participant's legally authorized representative).

The investigator and any designees are responsible for detecting, documenting, and reporting events that meet the definition of an AE or SAE as well as other reportable safety events. Investigators need to document if an SAE was associated with a medication error, misuse, or abuse.

Investigators remain responsible for following up AEs, SAEs, and other reportable safety events for outcome according to Section 8.5.3. The investigator, who is a qualified physician, will assess events that meet the definition of an AE or SAE as well as other reportable safety events with respect to seriousness, intensity and causality.

8.5.1 Time Period and Frequency for Collecting AE, SAE, and Other Reportable Safety Event Information

All AEs, SAEs, and other reportable safety events that occur after the participant provides documented informed consent, but before randomization, must be reported by the investigator if they cause the participant to be excluded from the study, or are the result of a protocol-specified intervention, including, but not limited to washout or discontinuation of usual therapy, diet, placebo, or a procedure.

Base Study:

From the time of randomization through 14 days following the first vaccination(s) and from the time of any subsequent vaccination(s) through 14 days thereafter, all AEs must be reported by the investigator. All SAEs and other reportable safety events that occur from the time of randomization through 6 months following the last vaccination must be reported by the investigator, regardless of whether the events are considered to be vaccine-related by the investigator.

Extension Study:

SAEs and death will be collected from the first dose of vaccination until 1 month after the last dose.

V503-064-03 FINAL PROTOCOL 24-SEP-2024

Base Study and Extension Study:

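### Non-solicited injection-site AEs are collected for Days 1-15 but compared with placebo only for Days 1-5, so non-serious ones starting on Days 6-15 get no between-group interval

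*Combined protocol and SAP*

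**What the plan says.** **Collection.** Section 4.1 follows "any other injection-site AEs and systemic AEs Days 1 through Days 15 following each vaccination". The vaccination report card in Section 8.4.4 records "Any other injection-site or systemic AEs Day 1 through Day 15 postvaccination", and separately "Solicited injection-site AEs (redness/erythema, swelling, and tenderness/pain) Day 1 through Day 5 postvaccination". Section 8.5.1 sets the investigator's duty over the same period: from any "subsequent vaccination(s) through 14 days thereafter, all AEs must be reported by the investigator". With the day of vaccination counted as Day 1, that is Days 1-15.

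**Analysis.** Section 9.6.3 leaves the windows to its table: "Detailed endpoints and day ranges are summarized in Table 7". There, the Tier 2 row for non-solicited local events is "Other injection-site AEs (incidence ≥1% of participants in either group) during Days 1 through 5 postvaccination". The severe injection-site row has the same Day 5 limit. Footnote (a), which hangs on the heading of the endpoint column, gives the day ranges as "injection-site AEs and maximum temperatures Days 1 through 5 postvaccination; systemic AEs Days 1 through 15 postvaccination". Entry to Tier 2 depends on frequency: "Membership in Tier 2 requires that at least 1% of participants in any treatment group exhibit the event". Only Tier 2 carries a 95% CI for the difference from placebo, because the protocol names no Tier 1 events.

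**Endpoint list.** Section 9.4.3 lists solicited injection-site AEs for Days 1-5 but has no line for non-solicited ones, although Table 7 analyses them. No section explains why their analysis window is shorter than their collection window.

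**The concern.** Take a participant who notices an injection-site nodule on Day 8. He writes it on the card and the site must report it, yet Table 7 stops counting injection-site events at Day 5. A systemic complaint starting on the same day and written on the same card is compared with placebo over the full 15 days. The plan thus treats two kinds of event from one source differently and gives no reason.

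Safety and tolerability is listed under the primary objective. Section 4.2.2 says placebo is there partly so that safety profiles can be compared. The vaccine is aluminium-adjuvanted (Section 2.2.1) and the comparator is saline (Table 1), so local tolerability is a natural place to look for a difference. At stake is the completeness of the local-reaction comparison. The efficacy conclusions are not touched.

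**Working it through.** **1. Windows side by side.**

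| Event type | Collected | Compared with placebo (Tier 2) |
|---|---|---|
| Solicited injection-site AEs | Days 1-5 (8.4.4) | Days 1-5 |
| Other injection-site AEs | Days 1-15 (4.1, 8.4.4, 8.5.1) | Days 1-5 |
| Systemic AEs | Days 1-15 (4.1, 8.4.4, 8.5.1) | Days 1-15 |
| SAEs | Randomization to 6 months after dose 3 (4.1) | Days 1-15; vaccine-related ones at any time |

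Only the second row has an unexplained gap for non-serious events. Days omitted: 15 - 5 = 10 of 15 after each dose.

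**2. A non-serious injection-site AE first appearing on Day 8, traced through Table 7.**
- Solicited, other and severe injection-site rows: too late, since each stops at Day 5.
- Systemic row: the window fits, but the event is local.
- SAE rows: the event is not serious.
- Tier 3, maximum intensity of injection-site AEs: limited to Day 5 by footnote (a).
- Tier 3, AEs by SOC: the row states no window. Footnote (a) read literally cuts injection-site AEs at Day 5 here too; read loosely, the event appears as a count without an interval.
- Tier 3, new medical conditions: too early, because Sections 4.1 and 8.1.4 define these as falling outside Days 1-15.

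The same event on Day 20 could be summarised as a new medical condition. On Day 8 it has no row that clearly applies. Pain, swelling or redness starting on Days 6-15 meets the same gap, because the solicited row also ends at Day 5.

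**3. The plan's own safety figures.** Section 9.9.3 takes 525 vaccine recipients.
- At least one SAE at a rate of 0.5%: 1 - 0.995^525 = 0.928 (stated 93%).
- Upper 95% bound if none is seen: 1 - 0.05^(1/525) = 0.569% (stated <0.6%).

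Both reproduce. The point does not depend on them; they confirm the denominator used below.

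**4. Tier 2 threshold.** 1% of 525 = 5.25, so 6 participants are needed: 5/525 = 0.95% fails and 6/525 = 1.14% passes.

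**5. Illustration.** The documents give no late-onset rate, so the risks here are assumptions for a single term first appearing on Days 6-15 in the vaccine group. The last column is the binomial chance of 6 or more among 525.

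| Assumed risk | Expected (525 x risk) | Chance of 6 or more |
|---|---|---|
| 0.5% | 2.6 | 5% |
| 1% | 5.25 | 43% |
| 2% | 10.5 | 95% |
| 3% | 15.75 | 99.9% |

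Miettinen-Nurminen 95% intervals for assumed counts against 0/525 on placebo:
- 6/525: difference 1.14% (0.41% to 2.47%).
- 10/525: difference 1.90% (1.04% to 3.47%).

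Under the present Table 7, neither interval would be produced for a non-serious local term confined to Days 6-15.

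**The case against.** The best defence is that Day 5 is deliberate. It appears in all three Tier 2 injection-site rows, in footnote (a), and in the 9.6.3 text on solicited and severe events, and collecting more than is compared is not in itself an error. It is probably right that the cut was meant. But no reason is given for applying it to events deliberately followed to Day 15. Section 4.2.1.3 says the safety assessments match those of previous studies; that does not justify the analysis window, and a retained Days 1-5 summary would protect comparability.

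Three further objections stand and limit the point.

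- **Primary endpoints.** A reader might infer that late local reactions drop out of the primary safety endpoints. The documents do not support that. Section 3 lists solicited injection-site AEs, systemic AEs and SAEs, so non-solicited local events were never among them. There is also no safety hypothesis. What is lost is a Tier 2 interval.
- **Other coverage.** Serious local reactions remain in the SAE rows, and non-serious ones may appear in the SOC summary. That coverage is ambiguous rather than plainly absent.
- **Size.** A reader might infer that two thirds of the events are lost, or that 5 to 16 vaccinees are omitted (525 x 1% to 525 x 3%). The first figure is a share of calendar days. The second rests on an assumed rate and is an upper bound even then, because anyone with the same term on Days 1-5 after any dose is already counted. Its low end, 5 of 525, would also miss Tier 2. The cut applies to both groups, so nothing in the documents shows which way the between-group difference would move.

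**Conclusion.** The concern holds as a mismatch between what is collected and what is compared. Non-serious injection-site AEs starting on Days 6-15 get no Tier 2 comparison with placebo, do not qualify as new medical conditions, and have an uncertain place in Tier 3. This follows from the text alone and needs no assumption about rates.

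Its consequence is moderate at most. It concerns non-serious events outside the listed primary safety endpoints, and the number affected cannot be estimated from the documents. The intervals above rest on assumed counts and show only what would go unreported. The 1% threshold applies to each term, so late events spread over several terms might get no interval even with the longer window. The change is still worth making, because the data are already in hand and the present rule leaves them without a clear home.

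**What to change.** 1. In Table 7, set the row for other injection-site AEs to Days 1-15, and state that pain, swelling or redness with onset on Days 6-15 counts there as a non-solicited event. Keep Days 1-5 for the three solicited terms.
2. Apply Days 1-15 to severe non-solicited injection-site AEs and to the matching maximum-intensity summary. Appendix 3 (Section 10.3.5) evaluates redness and swelling by size only through Day 5, so say that later-onset redness and swelling take their grade from the general intensity scale there.
3. Change footnote (a) to: *solicited injection-site AEs and temperatures, Days 1-5; other injection-site and systemic AEs, Days 1-15*.
4. Add non-solicited injection-site AEs, Days 1-15, to Section 9.4.3.
5. Keep a Days 1-5 summary for comparison with earlier studies.

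If the shorter window is intended, the minimum is to give the reason and say where events starting on Days 6-15 will be reported.

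Cost: edits to a few table rows, a footnote and an endpoint line, one more summary, and slightly higher injection-site AE percentages. No new data are needed. Section 9 allows changes to non-confirmatory analyses before unblinding or final database lock to go into the sSAP; after that, the summary can be given in the CSR, labelled post hoc.
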